Monitoring and blunting coping tendencies have also been shown to influence the extent to which individuals prefer to pay close attention to their wellbeing or avoid thinking about it (Murris & Van Zuuren, 1992; Miller, 1987). Those who employ monitoring to cope with health problems will actively seek out health information, whereas those who employ blunting will adopt distraction strategies in order to actively avoid health information (Miller, 1995). This information seeking preference is important as evidence suggests that acquisition of health information can lead to increased health anxiety in individuals who exhibit monitoring coping preferences (Miller, 1995). In the case of menopausal symptom monitoring, women's attention is drawn to information about their menopausal wellbeing, which may be anxiety provoking. Therefore, this measure will help us understand whether symptom monitoring is more or less effective as an intervention for women, depending on their health information-seeking preferences.

It is important to establish for whom symptom monitoring might be most helpful, or conversely taxing or even harmful should it challenge a dispositional tendency to avoid focusing on wellbeing. Indeed, coping style and neuroticism have both been associated with increased health anxiety following the procurement of health information (Lagoe & Atkin, 2015; Miller, 1987). Therefore, health anxiety will also be measured during this research to explore whether symptom monitoring influences it, and whether this effect is related to neuroticism or coping preferences.

A third objective is to investigate whether participants attribute the act of monitoring to any perceived improvements, or whether participants attribute other elements of research participation to their improved health (i.e. increased menopausal awareness), or whether participants do not perceive any improvements whatsoever. Studies which have included symptom monitoring as a control intervention often speculate that involvement in research is responsible for the positive outcomes found in the control group, rather than symptom monitoring in itself (Borud et al., 2010). However, these studies rarely provide data on this assumption. Therefore, the present study aims to establish whether participation in menopausal research per se improves wellbeing, regardless of what that participation entails.

Summary of objectives:

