This study will employ a 2-arm randomised controlled trial, including 1 symptom monitoring intervention group and 1 non-monitoring control group. The main analysis will be a 2 by 2 mixed between/ within-subjects ANOVA. The between-subjects component will compare symptom differences between the symptom monitoring intervention group and the usual care control group. The within-subjects component will compare symptom changes between baseline and after 2-weeks of daily symptom monitoring, and between baseline and after an interval of 2 weeks without monitoring, in the control group. The interaction will establish whether symptom changes differ over time according to whether women are in the symptom monitoring or control group. It is expected that improvements in well-being will occur over time in the symptom monitoring group, in comparison to the control group e.g., positive reactions will increase from baseline, whereas negative reactions will decrease. Symptom reports will be collected using the DRK (Boivin & Takefman, 1995). The intervention group will record their symptoms at baseline and every day for 2-weeks (although only baseline to follow up changes will be subject to analysis), the control group will record their symptoms at baseline and after an interval of 2-weeks with no daily monitoring. The DRK has been used previously in randomised trials of women's reproductive health (e.g., Boivin & Takefman, 1995; Ockhuijsen et al., 2014) to establish the effects of symptom monitoring. This research will take place electronically, questionnaires will be presented to participants in the form of JISC Online Surveys and accompanying information will be attached to emails as Word documents. This study has been designed in this way in response to the ongoing 2020 COVID-19 pandemic. The study admin will be managed by [name] via a dedicated USW email address: [contact].

Research design figure:

All participants:

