Participants in the intervention group will be invited to monitor their physical and emotional symptoms every day for 14-days using the Daily Record Keeping form (DRK; Boivin & Takefman, 1995), administered via JISC Online Surveys. **See Appendix 4 to view the daily DRK survey in Word document format. The online DRK survey can be viewed as it's presented on JISC Online Surveys via this link:** <https://southwales.onlinesurveys.ac.uk/daily-record-keeping-form-preview>. At 10am each day of the intervention period, participants in the intervention group will be sent an email asking them to complete the DRK survey by the end of the day- they will also receive text message reminders to complete the DRK at 5pm each day, unless they opt out of reminders. Both the email and text reminders will include a link to the online DRK. Participants can opt out of text message reminders at any time by emailing [name] requesting to opt out. Once participants have returned DRK surveys every day for 14 days, on the 15th day they will be asked to complete the follow-up survey within 24 hours. Once they have returned the follow-up survey they will be sent their £20 gift voucher via email. **See Appendix 5, page 1 to view a template of the daily DRK email reminders, see Appendix 5, page 2 to view a template of the text message reminders. See Appendix 6, page 1 to view the email template advising intervention group participants of their group allocation, and instructing them to complete the DRK survey each day for 14 days.** The online text messaging platform ClickSend will be used to manage the scheduling of daily text message (www.clicksend.com) See the section below titled "Data collection tools" for a more detailed explanation of the measures used in this study.

Control group:

Participants in the control group will not monitor their symptoms daily for 14-days and will instead be instructed to carry on as usual during the 2-week period, while the intervention group are monitoring. This group will complete all measures (including the DRK) at baseline and at follow-up on the 15th day only. **See Appendix 6, page 2 to view the email template advising control participants of their group allocation, and instructing them to carry on as usual for 14 days. If they indicated on the baseline survey that they are**

FACULTY OF LIFE SCIENCES AND EDUCATION FACULTY ETHICS SUB GROUP APPLICATION FORM

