9. MATERIALS AND METHODS

This study will use electronic means (online survey, email) and participants will receive a £20 Amazon voucher for completed participation. No face to face contact will occur between the research team and research participants. Participants will predominantly be recruited using JISC's online platform for connecting researchers with study participants (www.callforparticipants.com), as well as social media sites including Facebook and Instagram. Using these platforms, a research poster will be used to attract participants to the study and provide interested participants with a link to the screening questions, information sheet, consent form, and baseline survey. **See Appendix 7 to view the recruitment poster as it will be presented on www.callforparticipants.com, and shared on social media sites.**

The baseline survey (**see Appendix 1**) will collect the email addresses of interested participants. After submitting the baseline questionnaire, participants will be contacted via email with details about their group allocation and further instructions i.e. intervention participants will be instructed to complete 5-minute daily surveys each day for 14 days (see **Appendix 6, page 1** for instruction email template for intervention participants), whereas control group participants will be asked to continue as usual for 14 days (see **Appendix 6, page 2** for instruction email template for control participants). After the 14-day period both groups will be asked via email to complete the follow-up survey (**see Appendix 6, page 3**). The information sheet (**see Appendix 8**) and consent form (**see Appendix 9**) will precede the baseline survey and will provide full information about the nature of the study and details about what the participants in each group will be asked to do, including eligibility for the £20 incentive for taking part. The methodology for supplying participants with vouchers via email has been used in a previously approved study with no problems raised (ethics reference: 200401HR).

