- **Perceived effects of research engagement:** Three items (to be completed after the 2-week research period) will assess whether research participation has led to any perceived improvements in emotional and physical well-being: "Since your engagement in this research, what changes have you noticed in your physical or emotional well-being? "If you have experienced any changes, why do you think these changes occurred?" and "what impact has participating in this research had on your physical or emotional well-being?". These items will allow for more specific assumptions to be made about whether the use of symptom monitoring in research is attributed to perceived improvements, and whether researchers employing symptom monitoring as a control intervention should be wary of this occurrence. **To view how the research engagement questions will be presented on the follow-up**

FACULTY OF LIFE SCIENCES AND EDUCATION
FACULTY ETHICS SUB GROUP APPLICATION FORM

survey, see Appendix 3, page 8.

- **Covid-19 experience question:** A final qualitative item will also be used to assess participants' experiences in dealing with the menopause during the Covid-19 pandemic: "Experiencing the menopause during the Covid-19 pandemic might be especially challenging for some women. Please use this space to tell us more about this experience if you wish. E.g., did you feel able to consult a GP when you needed to? Did any changes due to work restrictions or changes in home circumstances feel different because of the menopause? Did the menopause make you feel more or less able to cope?". This item was included in order to gain perspective on the wider context in which this research is taking place, in order to understand how the 2020 pandemic has impacted research findings. **To view the Covid-19 experience question as it will be presented on the follow-up survey, see Appendix 3, page 8.**

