Inclusion criteria: this study will involve adult females, who report at least 2 hot flushes per day, with self-reported peri- or post-menopausal status. Women taking menopause-specific treatments (e.g. HRT or anti-depressants) are included in this study provided they reach the criteria for hot flushes and are otherwise healthy.

Exclusion criteria: participants will be screened out of the survey if they answer no to the following questions, which will be presented before the information sheet, consent form and main survey: "Are you over the age of 18?", "Are you experiencing at least 2 hot flushes per day?", and "Are you experiencing either perimenopause or menopause?"

Additionally, care will be taken to identify and exclude outliers from analyses, especially when considering the data of those who say they have been diagnosed with chronic or severe conditions with symptoms overlapping with menopausal symptoms, including chronic fatigue syndrome, fibromyalgia, cancer, heart

**FACULTY OF LIFE SCIENCES AND EDUCATION
FACULTY ETHICS SUB GROUP APPLICATION FORM**

disease, thyroid disorders, depression and other mental illnesses. As the research team is not medically trained, we are not able to ascertain definitively if women do have any medical conditions. However, women will be informed in the information sheet that they should not participate if they have these conditions for the reason stated above, and those who report such conditions in the demographic and medical history will be statistically assessed with caution using univariate and multivariate analyses, and data from these individuals will be excluded where necessary. Participants who do not complete all study materials or comply fully with the experimental protocol will also be excluded from analyses. Participants who report demographic characteristics that have been related to poorer health will also be assessed as covariates. Differences in symptoms between groups according to employment status, living status and relationship status will be analysed to understand variances in health between these groups. This is because unemployed, or single, or individuals who live alone are more likely to report poorer health than others.

Power analysis:

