Although research participation will not be anonymous, as interested participants will provide their email addresses to the lead researcher via the baseline survey (which will be advertised on www.callforparticipants.com) participants will be assured that their responses to the research materials will be kept entirely confidential. Participants will be made aware that they cannot be identified in any write up, presentation or publication of results of the study. If participants are uncomfortable with sharing such information, they will be reassured that they do not have to take part, and that if they change their mind about their participation, they can close down the survey at any point before submission and any information collected will be deleted or destroyed. This information will be reiterated on the information (**Appendix 8**) and debrief sheets provided at the beginning and end of the research surveys (**see Appendix 12**).

Survey participants will be asked to provide sensitive data (i.e. email addresses, menopausal status, menopausal symptoms, date of last menstrual period), and they will be advised of this via the information sheet (**See Appendix 8**) that sensitive information (and the type of sensitive information) will be asked of them prior to taking part in the study. Participants will be advised that they can withdraw their data from the study at any point up until they receive their £20 Amazon incentive.

To withdraw, participants will be instructed to email [name] with confirmation that they wish to withdraw their data. This information will be included in the information sheet (**Appendix 8**) and repeated in the debrief sheets (**see Appendix 12**). On the consent form (**Appendix 9**) participants will be asked to confirm that they understand they can withdraw their data up until they receive their incentive.

The information sheet will also state that if participants drop out of the study, the information they have submitted up until that point will be retained unless the participant withdraws prior to data analyses. Potential participants will be notified of their rights to withdraw their data, and that data will be retained if they do not give notice of their withdrawal, using this using the following statement:

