Uncertain				
Angry				
Worried				
Sleeping problems				
Weight gain				
Joint aches				
Low energy				
Hot flushes				
Stress/ anxiety				
Night sweats				
Low mood				
Brain fog				
Loss of sex drive				
Headaches				
Period changes				
Skin changes				
Vaginal dryness				
Urinary changes				
Painful sex				

FACULTY OF LIFE SCIENCES AND EDUCATION
FACULTY ETHICS SUB GROUP APPLICATION FORM

Bloating				
Poor concentration				
Itchy skin				
Digestive issues				
Memory loss				
Irregular heartbeat				
Breast pain				
Brittle nails				
Hair loss				
Electric shock sensations				
Muscle tension				
Body odour				
Allergies				
Burning tongue				
Other				

7b. If you selected "other" in the question above, please type what it was (type n/a if this does not apply to you):

.....

8. Since your engagement in this research, what changes have you noticed in your physical or emotional well-being?

.....

8b. If you have experienced any changes, why do you think these changes occurred?

.....

8c. What impact has participating in this research had on your physical or emotional well-being?

.....

**FACULTY OF LIFE SCIENCES AND EDUCATION
FACULTY ETHICS SUB GROUP APPLICATION FORM**

9. Experiencing the menopause during the Covid-19 pandemic might be especially challenging for some women. Please use this space to tell us more about this experience if you wish. E.g., did you feel able to consult a GP when you needed to? Did any changes due to work restrictions or changes in home circumstances feel different because of the menopause? Did the menopause make you feel more or less able to cope?

.....

To view this survey as it will be presented on JISC Online Surveys, please follow this link:

<https://southwales.onlinesurveys.ac.uk/follow-up-questionnaire-preview>

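### The question of for whom monitoring is taxing or harmful would be answered only from women who complied fully; daily forms from the others are kept but not summarised

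*Combined protocol and SAP*

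**What the plan says.** - **The question.** Section 7 (Aims and objectives) wants to know for whom monitoring helps, or is "conversely taxing or even harmful should it challenge a dispositional tendency to avoid focusing on wellbeing". It plans to measure health anxiety and relate it to coping style and neuroticism.
- **Who is analysed.** Section 10: "Participants who do not complete all study materials or comply fully with the experimental protocol will also be excluded from analyses". The sentence is limited neither to one analysis nor to one arm.
- **Which data are analysed.** Under section 8 the monitoring arm completes the Daily Record Keeping form (DRK) every day, "although only baseline to follow up changes will be subject to analysis". Section 22 lists a 2x2 mixed ANOVA, regressions and correlations. It has no missing-data method, comparison of dropouts with completers, or harm summary.
- **Who gets the follow-up survey.** Section 8 (Intervention group): "Once participants have returned DRK surveys every day for 14 days, on the 15th day they will be asked to complete the follow-up survey". Section 9 is looser: "After the 14-day period both groups will be asked via email to complete the follow-up survey". Section 15 and Appendix 13 also describe the link as going to everyone. The survey (Appendix 3) carries the health-anxiety items and open questions such as "What impact has participating in this research had on your physical or emotional well-being".
- **What is kept.** For a woman who drops out, section 14 says "the information they have submitted up until that point will be retained unless the participant withdraws prior to data analyses".
- **What happens if harm is suspected.** Under section 14 the supervisors are consulted if data point to a negative effect of the DRK on individuals, with escalation to research governance.

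**The concern.** The women about whom section 7 worries, those inclined not to dwell on their health, are plausible candidates to stop filling in a daily symptom form. If some stop for that reason, the exclusion rule removes them from the analyses meant to find them. The third hypothesis (section 8) compares monitors with blunters in the intervention arm at follow-up, so it too would be tested only in women who finished. Monitoring could then look better tolerated than it was among all women asked to do it, and the report would give no sign of this. Forms from the days before a woman stopped are held, but no planned outcome or harm analysis uses them. The reliability check of the loneliness items in section 9 may draw on some daily forms, but it does not look at harm.

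**Working it through.** **Inputs.** 52 completers needed, 33% attrition, 78 randomised, 39 per arm; attrition rates of 10%, 31% and 34.5% (section 10, Power analysis). Voucher terms: 14 daily forms and the follow-up survey, each within 24 hours (section 27). DRK items scored 0-3 (Appendix 1).

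**1. The plan's own figure.** 52 / (1 - 0.33) = 77.6, so 78. This reproduces the stated sample size. Per arm, 39 - 26 = 13, and 13/39 = 33%.

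**2. Monitored women left out, by attrition rate.** 39 x 0.10 = 3.9; 39 x 0.31 = 12.1; 39 x 0.33 = 12.9; 39 x 0.345 = 13.5. That is about 4 to 13 women. For a summary of daily forms 13 is an upper figure, because some may return no daily form. The 34.5% rate is counted from women who agreed to take part, so it may include women who never started.

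**3. Exclusion through late or missed surveys alone.** The plan does not define full compliance. If it means the section 27 rule, a monitored woman must return 14 + 1 = 15 surveys on time and a control woman 1. With on-time probability p per survey (assumed, independent), the expected number excluded is 39 x (1 - p^15) in the monitoring arm and 39 x (1 - p) in the control arm.

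| p | p^15 | Monitoring, excluded of 39 | Control, excluded of 39 |
|---|---|---|---|
| 0.99 | 0.860 | 5.5 | 0.4 |
| 0.98 | 0.739 | 10.2 | 0.8 |
| 0.97 | 0.633 | 14.3 | 1.2 |

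The excluded group can therefore mix women who missed one form with women who stopped, which is why a summary needs the day of last form and the number returned.

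**4. What completer-only reporting could hide.** The DRK has 24 emotion items, 8 of them positive, leaving 16 negative; 16 x 3 = 48, so a simple sum runs 0-48. If the mean change is D points worse in non-completers, the completer mean looks better than the all-monitored mean by D x 13/39. For D = 2, 4 or 8 (assumption; the documents give no basis for D) that is 0.7, 1.3 or 2.7 points.

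**5. What a summary of the held forms could show.** The 95% half-width for a mean change is t(0.975, n-1)/sqrt(n): 0.60 SD at n = 13 and 1.59 SD at n = 4. If 0 of 13 worsened, the one-sided 95% upper limit would be 1 - 0.05^(1/13) = 20.6%.

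**The case against.** Four points can be made for the plan.

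*There is a harm provision.* The section 14 escalation step responds to DRK data on individuals and is not confined to completers. This stands: a reader who infers that the plan ignores harm would be wrong. But the step names no summary, population, threshold or timing, and reports nothing to readers of the trial.

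*Women who stop can still report.* A reader of section 8 might infer that a woman who misses forms is never sent the open questions. The documents do not support that: sections 9 and 15 and Appendix 13 send the survey to all, and section 8 can be read as describing timing. What remains is that her answers would be excluded under section 10. That sentence sits beside text on outliers and does not mention free-text items, so a narrower intent is possible, but its wording is unqualified.

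*Retention may imply use.* Keeping partial data until analysis leaves room for some use of it, and the participant-facing statement and Appendices 8, 9 and 12 were not available for this review. In the text available, no outcome or harm analysis uses it.

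*A descriptive table proves little in an exploratory study.* This is largely fair. The table has no control group and few women, and a table by completion status alone would not address for whom monitoring is harmful. It therefore needs the baseline coping and neuroticism scores, which are collected before any woman can stop.

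**Conclusion.** The concern holds in limited form. As written, the harm question of section 7 and the third hypothesis would be answered from full compliers only. About 13 of 39 monitored women fall outside at the planned attrition, if losses are equal in the two arms. Under the section 27 reading about 5 to 14 fall outside through timeliness alone, given independent on-time rates of 99% to 97%.

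Two stronger readings are not supported. Nothing shows that women will stop because of distress; the documents give no figure for this. Nor would the held forms reveal why a woman stopped: they end when she does and record no reason. They can show only whether her scores were rising beforehand. The DRK also records negative emotions rather than health anxiety itself. The change is worth making because it is cheap and bears on the plan's own question, but it does not alter the main estimate.

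**What to change.** Keep the 2x2 ANOVA.

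1. In sections 8 and 22, add a descriptive summary of day 1-14 DRK negative-emotion scores and change from baseline, for all monitored women who returned at least one daily form and have not withdrawn their data. Show completers and non-completers separately, with day of last form, number of forms returned, and baseline MBSS (monitor/blunter) and neuroticism scores for each group.
2. Alongside it, summarise any follow-up health-anxiety scores and open-question answers from women who missed forms.
3. In section 10, add to the exclusion rule: *except from this descriptive summary*.

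The negative-emotion score must be defined in advance. The 16-item sum is one option, but section 9 describes separate emotion facets and no such total.

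**Cost.** A short descriptive output from data already held, with no new collection or contact. It cannot show that monitoring caused a change or why a woman stopped, it misses women who return no daily form, it is imprecise, and it leaves completer-only bias in the ANOVA. The sponsor should confirm that the information sheet's retention statement covers this use.

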An a priori power analysis was conducted using G*Power 3 (Faul, Erdfelder, Lang, & Buchner, 2007) to test the difference between two independent group means (accounting for special, main effects, and interactions) using a two-tailed test, a medium effect size ($d = .40$) and an alpha of .05. Results suggested that a total sample of 52 participants with two equal sized groups of 26 was required to achieve a power of .80.

Medium effect sizes were estimated based on Cohen's (1962) conventional values because these values were derived from studies specific to psychological research (Aguinis, & Harden, 2009). Furthermore, medium effect estimates, rather than small estimates, were used for this research because this study is exploratory and small effects on symptom frequency might not be noticeable to participants. Small effects might imply that symptom monitoring as an intervention to help reduce menopausal symptoms may lack meaningful benefit.

Hoerger (2010) found evidence that at least 10% of participants will drop out of internet mediated research and such studies have high attrition rates. Furthermore, several studies have provided data on attrition rates of studies which employ a 2-week intervention period. Lancastle and Boivin's (2008) feasibility study aimed to establish whether a brief coping intervention (positive reappraisal coping intervention; PRCI) was acceptable and practical when evaluated in the context of a randomised trial. Of the 84 women who agreed to participate in the study 55 (65.5%) completed all measures, suggesting an attrition rate of 34.5%. Moreover, Lancastle's (2006) study also evaluated the PRCI alongside a positive mood inductive intervention, and a daily monitoring control group; this research reported a 31% attrition rate.

Therefore, taking into account average attrition rates from internet mediated research (10%), as well as studies which have utilised a 2-week intervention period (33%), it was decided that the proposed study will use a total sample of 78 participants with two equal groups of 39.

11. HAVE NATIONALLY APPROVED / REGULATORY BODY GUIDELINES BEEN FOLLOWED IN PREPARING THIS PROTOCOL?

(E.g. Association of the British Pharmaceutical Industry Guidelines (1983), Royal College of Physicians Guidelines, The Declaration of Helsinki, British Psychological Society guidelines, BERA, etc.). If so, please specify.

- Faculty of Life Sciences and Education Ethics Committee

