22. DATA ANALYSIS / STATISTICS

Please describe the arrangements for analysing your data (qualitative and quantitative). Where appropriate discuss what data/statistical analysis will be completed. Where used, please remember to discuss sample size and how the sample size was decided upon.

2 x 2 mixed between-within ANOVA:

The main analysis will include a 2x2 mixed between-within ANOVA to assess differences in symptoms among the symptom monitoring and control groups before and after the 2-week research period. The between-subjects component will encompass the differences in symptoms between the control and intervention groups; the within-subjects variable refers to differences in symptoms before and after the 2-week study period. It is expected that after 2 weeks of symptom monitoring the intervention group will exhibit a greater reduction in symptoms in comparison to the control group (i.e., a significant group x time interaction). As discussed, a power analysis was calculated to identify the minimum sample size needed to detect moderate effects, resulting in the decision to recruit 78 participants, with 39 participants being randomised into each group.

Regressions:

Multiple regressions will explore whether help-seeking intentions as continuous variables as predicted by symptom monitoring group (dummy coded), self-efficacy in patient-doctor communication, self-efficacy in shared decision making, health and symptom awareness, and self-efficacy in goal orientated behaviour, health anxiety, and menopausal symptom changes.

Logistic regressions will establish whether control or intervention group membership (as measured as a dichotomous “Invention/Control” variable) is predicted by health anxiety, variances in emotions and symptoms, help-seeking intentions, self-efficacy in patient-doctor communication, self-efficacy in shared decision making, health and symptom awareness, and self-efficacy in goal orientated behaviour.

Correlations:

FACULTY OF LIFE SCIENCES AND EDUCATION
FACULTY ETHICS SUB GROUP APPLICATION FORM

Correlations will also be computed to assess for associations between certain variables. For example, higher neuroticism X higher negative emotions.

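### The stated inputs (two independent means, two-tailed, d = .40, alpha .05) need 100 per group for 80% power, not 26; with 52 completers that comparison has about 29% power

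*Combined protocol and SAP*

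**What the plan says.** Section 10 (Power analysis) reports a G*Power calculation "to test the difference between two independent group means (accounting for special, main effects, and interactions"), two-tailed, with "a medium effect size ($d = .40$) and an alpha of .05". It concludes: "Results suggested that a total sample of 52 participants with two equal sized groups of 26 was required to achieve a power of .80". The total is then raised to 78 (39 per group), citing attrition of 10% in internet research and 33% in studies with a 2-week intervention period.

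Section 10 also says of the analysed set: "Participants who do not complete all study materials or comply fully with the experimental protocol will also be excluded from analyses".

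Section 8 states: "The main analysis will be a 2 by 2 mixed between/ within-subjects ANOVA". Sections 8 and 22 make the group x time interaction the test of the hypothesis. Section 22 rests the sample size on section 10: "a power analysis was calculated to identify the minimum sample size needed to detect moderate effects". No baseline/follow-up correlation is given in either section.

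**The concern.** The power sentence gives every input that a two-sample calculation needs, so it can be checked directly. For d = .40, 26 per group is far too few: the requirement is nearly four times larger. Using an approximation, rounding, or switching to a one-sided test (78 per group) cannot close that gap.

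This is the only quantitative basis for the sample size. The randomisation list of 39 numbers out of 78 was built on it, and section 22 cites it as showing that the trial can detect moderate effects. A reader who believes the power is 80% would take a non-significant result as fair evidence against a moderate benefit of monitoring. If the true power is near 29%, a real effect of d = .40 would be missed about 7 times in 10, and a null result would say little.

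**Working it through.** **Inputs, all from section 10 (Power analysis).** Two independent means, two-tailed, d = .40, alpha .05, target power .80, equal groups, stated n = 26 per group, attrition 33%, 78 randomised.

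**1. The stated calculation.** For n per group, the test statistic has 2n - 2 degrees of freedom and noncentrality d x sqrt(n/2). Power is the probability that its absolute value exceeds the two-sided .05 critical value.

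| n per group | noncentrality | critical t | power at d = .40 |
|---|---|---|---|
| 26 | 0.40 x sqrt(13) = 1.442 | 2.009 | .293 |
| 39 | 0.40 x sqrt(19.5) = 1.766 | 1.992 | .415 |
| 99 | 0.40 x sqrt(49.5) = 2.814 | 1.972 | .7997 |
| 100 | 0.40 x sqrt(50) = 2.828 | 1.972 | .804 |

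The plan's 26 per group is not reproduced; the answer is 100 per group. The smallest d with 80% power is 0.79 with 26 per group and 0.64 with 39 per group.

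**2. Where 52 could come from.** Section 10 does not show the G*Power routine or its output, so this is inference. Three routes return 52:

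- Fixed-effects F test, numerator df 1, f = .40, noncentrality f² x N. With two groups, N = 51 gives .7996 and N = 52 gives .807; with four groups, N = 52 also gives .807. For two equal groups d = 2f = .80. The mention of special effects, main effects and interactions fits this routine.
- Paired t test, d = .40: 52 pairs, power .808. That is 52 people each measured twice, not two groups of 26.
- Repeated-measures interaction, f = .20, r = .5, noncentrality f² x N x 2/(1 - r): N = 52 gives .807. This corresponds to a 0.80 SD difference in change, and it needs a correlation that the plan does not state.

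None of these is a comparison of two independent means at d = .40.

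**3. The analysed size.** 52/(1 - .33) = 77.6, rounded up to 78. Conversely 78 x .67 = 52.3. The inflation step is therefore consistent, and about 26 per group is what the plan expects to analyse after excluding non-completers and non-compliers.

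**4. The planned interaction.** In a 2 x 2 mixed ANOVA the group x time test is equivalent to a two-sample t test on change scores. Assume equal variance at both times and a difference in change of 0.40 expressed in units of that common SD. The SD of change is then sqrt(2(1 - r)), and the effective d is 0.40/sqrt(2(1 - r)). For example, r = .7 gives 0.40/0.775 = 0.516. The documents do not give r, so a range is shown:

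| assumed r | power, 26 per group | power, 39 per group | difference in change with 80% power, 26 per group | same, 39 per group |
|---|---|---|---|---|
| .3 | 22% | 31% | 0.94 SD | 0.76 SD |
| .5 | 29% | 41% | 0.79 SD | 0.64 SD |
| .7 | 45% | 61% | 0.61 SD | 0.50 SD |
| .8 | 61% | 79% | 0.50 SD | 0.41 SD |

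Simulation with 40,000 runs per cell agreed to within about .002. Setting 0.40/sqrt(2(1 - r)) equal to the d with 80% power (0.792 or 0.643) and solving for r gives r = .87 with 26 per group and r = .81 with 39 per group.

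**The case against.** The strongest reply is that the main analysis is the interaction, so 29% describes a different test. The figure of 52 may also have come from a repeated-measures interaction routine with f = .20, which is d = .40 halved, and r = .5. That route does reproduce 52, so the cause of the figure stays open and it may after all have come from the planned test. It does not rescue the sentence. Section 10 describes two independent means and states no correlation, and on this route 52 still corresponds to a 0.80 SD difference in change, twice the stated effect.

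Three further points have some force.

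- The interaction powers depend on how 0.40 is standardised. If it is in units of the SD of change, power is 29% or 41% (26 or 39 per group) whatever r is, so the r thresholds above apply only to the cross-sectional SD. That reading does not help the plan.
- With the 10% attrition that section 10 also cites, about 70 would remain (78 x .90 = 70.2, so 35 per group). Power for d = .40 in the two-means comparison is then 38%, still less than half the stated .80.
- The plan calls the study exploratory, and no claim of no effect is planned. That limits the harm, but section 22 still offers the calculation as showing adequacy for moderate effects, and a stated power that does not follow from its inputs needs correcting in an exploratory trial too.

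**Conclusion.** The point holds: the power statement is wrong as written. For the comparison and inputs that section 10 states, 80% power needs 100 per group. With 26 per group the power is 29%, and with all 39 per group it is 41%. These figures need no assumption beyond the usual two-sample t test.

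For the interaction the conclusion is conditional on r and on equal variances. With the cross-sectional SD as the unit, power for a 0.40 SD difference in change runs from 22% to 61% with 26 per group, and from 31% to 79% with 39 per group, for r from .3 to .8. It reaches 80% only at r of about .87 or .81 respectively. That .40 was entered as f is the likeliest explanation but is not established. The sample as set detects d of about 0.8, so the description of the target as medium, and the argument for it in section 10, do not match the number.

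**What to change.** **Section 10.** State which G*Power routine was run and whether .40 was d or f. Replace the result sentence with, for example: *52 completers (26 per group) give 80% power for d of about 0.8 and about 29% power for d = .40 in a two-tailed comparison of two independent means.* If f was meant, justify a target of d = .80.

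**Sections 10 and 22.** Give the detectable difference for the group x time test over a range of assumed correlations, naming the standardiser. With 26 per group this is about 0.94, 0.79 and 0.61 SD at r = .3, .5 and .7. Remove the unqualified claim that the sample detects moderate effects, and state that a non-significant result does not rule one out.

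**Cost.** Wording in two sections, and a less favourable stated detectable effect. Making the text correct needs no extra recruitment and no change to randomisation or conduct. Enlarging the trial would be a separate decision, and arises only if the authors do want 80% power for d = .40 in the two-means comparison: that means 200 completers, or 200/(1 - .33) = 298.5, rounded up to 299 randomised.
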